3.2.3 Estimating GAS infection incidence

To assess incidence of clinical GAS disease in the cohort throughout the study, all participants reporting symptoms suggestive of possible clinical GAS infection such as pharyngitis or pyoderma (but also including invasive infections), will be visited for an unscheduled visit where a clinical and

health-seeking history will be recorded, a swab, saliva and DBS taken, and treatment (or further management) will be delivered according to WHO guidelines or best local practice. Furthermore, at each scheduled visit, any individual identified with symptoms of clinical GAS infection will undergo the same process of history-taking, swabbing, treatment and follow up.

4 Selection and withdrawal of participants

4.1 Selection of participants

The study will enroll participants as individuals within households. Households will be identified using a process of random selection. No complete sampling frame of households exists for Sukuta, however GIS data exist from the 2013 census of The Gambia. These data will be utilized to obtain a random set of sampling locations stratified by population density. A list of GPS coordinates for the locations will be identified and for each location, the nearest household will be approached for participation. Each location on the list will be approached in order until the desired sample size is reached. Households will only be enrolled if all members of the household consent to participate in the study.

For the purposes of enrolment in the study, a household will be defined according to The Gambia Demographic and Health Survey 2013 definition: “a household [is] defined as a person or a group of related or unrelated persons who live together in the same dwelling unit(s) or in connected premises, who acknowledge one adult member as the head of the household, and who have common arrangements for cooking and eating.”

4.2 Eligibility of participants

Households and all individual participants must meet all of the inclusion criteria and none of the exclusion criteria to be eligible to participate in the trial.

Participants must meet all of the inclusion criteria and none of the exclusion criteria to be eligible to participate in the trial.

4.2.1 Inclusion criteria

Households must:

- Be within the boundary of Sukuta as determined by the 2013 census
- Have at least 3 members including at least one child under age 18

Individuals must:

- Provide signed (or thumbprinted) informed consent for study participation (obtained from a parent or guardian for children under the age of 18)
- Be willing and have capacity to participate and comply with the study protocol as judged by a member of the study team
- Be resident in the household, with no plans to move outside of the household during the period of study participation

4.2.2 Exclusion criteria

Households:

- Less than 50% of individuals living in the household, as defined by the The Gambia Demographic and Health Survey 2013 definition, provide consent to participate

Individuals:

- Consent not provided
- Has any condition or any other reason that may lead to difficulty or discomfort in obtaining all the necessary samples
- Is judged by the study team member to be unable or unlikely to participate and comply with the study protocol for the entire study period

4.3 Withdrawal of participants

A study participant will be discontinued from participation in the study if:

- Any clinical significant adverse event (AE), laboratory abnormality, intercurrent illness, or other medical condition or situation occurs such that continued participation in the study would not be in the best interest of the participant.
- Development of any individuals' exclusion criteria.

Participants are free to withdraw from the study at any time without giving a reason. Household heads are free to withdraw their household from the study at any time without giving a reason.

If an individual withdraws consent to participate in the study, or their participation is discontinued by the study team for any of the above reasons, this will not necessitate the withdrawal of the other members of their household if the discontinuation occurs after the first month (once MV1 visits commence) of the study. If an individual withdraws within the first month (before MV1 visits commence), it may be determined by the PI that the entire household be withdrawn and another household recruited as described above. If not possible or practical to recruit another household, the household with a withdrawn member may continue in the study.

4.3.1 Missed visits and visit windows

Household visits will be arranged for the same day of the month as the enrolment visits where possible, to within 14 days. For example if a household's enrolment visit (MV0) is on the 5th of March, their M1 visit will be arranged for 5th April, unless this coincides with a weekend, in which it may be delayed or brought forward (within 14 days either way) to a working day. Households will be reminded by phone by the study team a few days in advance of a study visit. They will be reminded that all household members should be present if possible. All possible efforts will be made to arrange the visit to be at a convenient time of day when all household members can be present. If the visit must be rearranged due to unexpected circumstances such as a funeral, the study team may rearrange the visit to another day (within 14 days of the required date where possible).

Where it is not possible to arrange a time when most household members are present, or if a household member is missed due to any other reason, the study team will attempt to collect the required samples from them within 7 days of the household visit where it is feasible.

For participants undergoing weekly visits for intensified swabbing, the visit will be arranged on any day of the next working week. If more than one weekend passes between weekly visits, then a visit will have been missed.

If a household or individual misses their visit and sampling windows, they will continue in the study according to all subsequent planned visits. Samples for the missed visit window will not be collected.

5 Study procedures and evaluations

5.1 Sensitization

Sensitizing potential study participants will precede the formal recruitment period to ensure that they are aware of the study as far in advance as is practical and therefore are given as much chance as possible to consider their potential involvement prior to providing informed consent. Sensitization will be approached using community and household/individual level strategies.

5.1.1 Community sensitization

Prior to any study recruitment, a meeting, or series of meetings, will be arranged with the village Alkalo and other key leaders within the community such as elders and community stakeholders to discuss the study, to sensitize the community to the study, and to answer any questions or concerns that may be raised. Details of the study will be provided by the study team and discussed, allowing for everybody present to gain full understanding of the purpose of the study, and the risks and benefits as outlined in the informed consent document. The study team will also ask the village leaders and stakeholders present to disseminate information about the study to the wider community.

5.1.2 Household and individual sensitization

Once a household has been identified from the GPS location on the potential household list (as described in section 4.1) members of the study team will approach the household to sensitize them to the study. At least two days in advance of the enrolment visit, the study team will approach the households to ask to speak with the head of the household. If they are willing, the study team will then sensitize the household head (and other household members present if they wish) to aspects of the study including the purpose, procedures, risks and benefits of participation. They will answer any questions that household members may have, and distribute copies of the informed consent document information sheet.

If the household and individuals meet the inclusion criteria, and the household head is potentially willing to participate, the study team will complete the sensitization log, and sensitization form with details of the household composition, including contact details. They will then make an appointment for an informed consent visit the following day (or another day at least 24 hours after the initial sensitization visit) and will then ask the household head to discuss the study with the whole household in advance of the next appointment, and come to a decision about whether the entire household would be willing to participate in the study.

5.2 Informed consent

At the informed consent visit (at least 24 hours after sensitization), the study team will discuss the study once again with the household head and other household members to confirm that they have understood the consequences of study participation and to answer any remaining questions. If all the inclusion criteria are met and none of the exclusion criteria are, the study team member will proceed to obtain informed consent from all household members.

If at the consenting visit, the study team member determines that the household does not meet the inclusion and exclusion criteria, or anyone in the household is not willing to take part, then they will not proceed with the consent process.

Once the desired sample size of 45 households have been consented, study recruitment will be complete. If any household withdraws consent, or cannot participate for any other reason after consenting, they may be replaced by another household (the next GPS location on the list). Individuals who were not present at MV0 and subsequent visits but wish to participate at a later time may provide informed consent and enrol at any later monthly visit.

5.2.1 Informed consent for adults aged 18 years or more

To obtain informed consent from the household members, in the presence of a literate witness, a member of the study team will translate the informed consent document (ICD), which is in English, line-by-line into the local language spoken by the consenting individual (e.g. Mandinka, Wolof or Fula). Once the entire ICD has been translated, the study team member will answer any questions that the individual may have. If the consenting individual remain willing to participate and to provide informed consent, the study team member will document their informed consent on the signature page of the ICD. The study team member will document the participant's name, the name of the head of household and the language of consent. If the participant is literate, they will be invited to write the date and time and then sign the ICD. If the participant is not literate, the witness will write the date and time and the participant will be asked to thumb-print the signature portion of the ICD. The witness will then date and sign to confirm that the participant voluntarily agreed to take part in the study. The study team member will then write the date and time and sign the section relating to the person obtaining consent.

5.2.2 Provision of assent by children aged 12-17 years

For children aged between 12 and 17 years inclusive, they will be asked to provide assent to participate in the study in addition to the informed consent provided by the child's parent or legal guardian. In order to do so, the study team member will explain the study in simplified form to the child in an age-appropriate way, and will answer any questions that they may have. They will then be asked to sign (or thumbprint) the "participant's assent" section. The parent or legal guardian will also be required to sign (or thumbprint) the ICD form for the child, as described in section 5.2.1.

5.2.3 Informed consent for children aged less than 12 years

If the participant is under the age of 18, the child's parent will be required to sign (or thumbprint) the ICD on their behalf. When documenting consent for the child, one of their parents or a legal guardian will be asked if they provide consent for the child to participate undergoing the same process as described in section 5.2.1. The study team member will write the child's name on the ICD under "participant's name", then they will write the name of the parent or guardian providing consent under the relevant section.

5.2.4 Confirmation of ongoing willingness to participate

A certified copy of the signed ICDs for every participant will be provided to them at the enrollment visit. Written consent is obtained only at the consent visit, but opportunities to ask further questions will be given at each visit and ongoing willingness to participate in the study will be confirmed verbally at each opportunity. It will be made clear at every point, that participation is voluntary, and they may decline to participate or withdraw consent to participate at any point without giving a reason.

5.3 Study household visits

5.3.1 Visit planning and logistics

Enrolment for the study will aim to commence 1-3 months before the expected start of the rainy season in 2021. Prior to the enrolment visit, the study team will identify all of the consented households and schedule their enrolment visits in the most logically practical way for the upcoming days and weeks in order to minimize travel, and evenly distribute the number of participants to be seen and sampled each day (Monday to Thursday). With 45 households to be seen within a month, and an average household size of 10, this will mean 2 to 3 household visits will be required each working day, with approximately 25 to 30 individuals seen each working day for the main cohort. Another team will perform the weekly visits for the intensified swabbing cohorts.

Prior to each visit day, the study team will call at least one household member, ideally the household head, to arrange the visit as scheduled, and to ensure that all household members will be present at the arranged time. If not possible that every household member is there, it may be necessary to go ahead with the visit without everyone present, but arrange for a study team member to reattend within the visit window to see the missing household member.

It may be necessary to move a visit at short notice due to public holidays, religious ceremonies, illness or other unforeseeable reasons. In such cases, the study team will make every effort to inform the study participants affected as soon as possible and to rearrange their planned visit (within the visit window – see section 4.3.1).

5.3.2 Enrolment visit (MV0)

At the enrolment visit (MV0), each individual will undergo a baseline survey including participant's sociodemographic data, medical history and social-mixing/behavioural factors. A physical examination will be carried out including a full body examination (taking care to maintain privacy) looking for any evidence of skin infections, and swabs will be collected from the oropharynx and from normal skin. Additionally, a salivary sample will be obtained, and blood will be taken for a serum sample and dried blood spot. Any individual who is exhibiting symptoms of pharyngitis (sore throat and pharyngeal inflammation) will be further examined and managed as they would be at an unscheduled visit for possible GAS infection (see section 5.3.4 below). Any individual who is identified as having evidence of pyoderma (bacterial skin infection involving pus or crusts), will have a wound swab taken, and will be provided antibiotic treatment according to WHO or local guidelines as appropriate. Any additional abnormal finding requiring further investigation or treatment will be managed according to local practice or an appropriate referral made according to the nature of the finding (see section 5.3.4).

Alongside the individual surveys, data will be collected for each household such as household setup, family relationships, sleeping arrangements, presence of mosquito nets, number of rooms, number

of buildings and access to water points. Environmental swabs will be taken from common touch points such as door handles and soft furnishings, and settle plates will be used indoors to investigate airborne transmission.

5.3.3 Monthly visits (MV1, MV2, MV3 etc. up to MV12)

Participants will be enrolled for 12 months undergoing an enrolment visit (MV0), then up to monthly visits (MV1, MV2, MV3 etc. up to MV12), though enrolment may occur at a visit later than MV0.

At and each monthly visit following enrolment, the study team will collect further survey data from each individual household member, collect an oropharyngeal and a normal skin swab, dried blood spot and salivary samples. Data collected will include updated socio-demographic information, social-mixing and behavioural factors and clinical examination findings. Any evidence of pyoderma will be swabbed and treated, and any other abnormal finding requiring further investigation or treatment will be managed according to WHO guidelines or best local practice or an appropriate referral made according to the nature of the finding. Additionally, any use of antibiotics or other medication, or any attendance at a healthcare setting since the previous visit will be recorded.

5.3.4 Unscheduled visits for possible GAS infection

At any point during a participant's enrolment in the study, they may develop symptoms consistent with a superficial GAS infection (acute pharyngitis or pyoderma), a severe GAS infection, or an acute reaction to a GAS infection such as acute rheumatic fever (ARF). This may occur, or be picked up, at a scheduled monthly or weekly visit, but could occur at any other time. If this occurs between scheduled visits, they will be asked to contact the on-call study nurse, who will take details of the complaint over the phone, and depending on the severity of the symptoms will arrange for the participant to be seen either urgently at the MRC Unit Clinical Services Department, or less urgently at their compound the next day (or as soon as reasonably possible). The study nurse will be able to consult with the PI or another delegated clinician for medical advice.

In the case of a non-urgent visit, the study nurse will collect data on the history of the complaint, any medication taken and other relevant information. They will perform a physical examination, including vital signs. If the symptoms are consistent with possible GAS infection (pharyngitis or pyoderma), then a study swab will be taken (throat or wound) for culture alongside a saliva sample and a dried blood spot test. Treatment will be provided for pyoderma according to WHO or local guidelines. For suspected pharyngitis, treatment will be provided empirically based on WHO or local guidelines, and then reviewed following the culture result.

In the case of urgent visits at the Clinical Services Department, a study team member will attend the ward to collect this data as soon as possible, and take the study swab if applicable (ideally prior to any antibiotic therapy). Any further investigations performed and treatment given by the clinical services team will be recorded. In the case of suspected invasive GAS infection, the patient would be admitted for treatment. A blood culture should be performed as part of clinical assessment and if GAS is identified, the isolate will be obtained from the clinical microbiology laboratory for further analysis including whole genome sequencing. In the case of invasive GAS or suspected ACF the study team would obtain a separate serum sample.

5.3.5 Weekly visits for households in the intensified incident GAS cohort

A subgroup of 16 randomly selected households will be selected to participate in the intensified incident GAS surveillance cohort. These households will be visited up to every week for 6 weeks during the second half of the study, in addition to their regular monthly visits at MV1, MV2 etc. The

purpose of this cohort is to investigate asymptomatic GAS carriage incidence with greater resolution (more frequent swabbing) than the main cohort. At the weekly visits they will undergo OPS and NSS. Additionally these households will be asked more detailed questions about social-mixing behaviours such as school, mosque and market attendance frequency in the form of a daily diary or similar. These data will be used in combination with WGS data from any GAS identified to inform the household transmission model.

At these visits the study team will complete a survey for all household members containing a brief medical history and physical examination, and a more extensive social-mixing behaviours section. Throat and normal skin swabs will be taken, and any symptoms identified managed as above (section 5.3.4).

5.3.6 Weekly visits for asymptomatic GAS (or GCS/GGS) carriers

All participants not already in the intensified incident GAS cohort, who's OPS or NSS grow GAS (or GCS/GGS) on culture at a monthly visit following a previous negative swab, will be classified as "new carriers" who will then be swabbed weekly until such time as 2 negative swabs in a row have been obtained from the same site that was positive i.e. a participant who's OPS was positive at MV1 will have weekly OPS until negative twice in a row, whereas a participant with a positive NSS will have weekly NSS.

At these weekly visits, only the household member who is a "new carrier" will be seen and swabbed, not the other household members. The study team will ask a brief medical history, perform a physical examination, and take the swab from the previous positive site. If the participant has developed any clinician symptoms potentially in connection with their positive swab, then they will be treated as a GAS infection case as described in section 5.3.4.

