- Clinical examination findings and features of clinical GAS infection

Secondary endpoints:

- Presence of risk factors for GAS carriage or disease at individual and household levels
- Seasonal variation in GAS carriage and infection prevalence
- GAS *emm* type
- Groups C and G streptococcal prevalence and incidence
- Quantification of bacterial presence by qPCR
- GAS serological responses (including seroprevalence and fold-change in antibody titres in response to asymptomatic carriage and clinical infection).
- GAS presence on household swabbing and settle plates
- GAS antimicrobial sensitivity

Description of Study Design: A prospective cohort study within households in Sukuta, The Gambia, will be conducted. A total of 45 households will be recruited, including every household member as individual participants (resulting in approximately 450 participants).

Participants will be enrolled for 12 months, covering one full rainy season, undergoing an enrolment visit (MV0), then monthly visits (MV1, MV2, MV3, etc. until MV12). At each visit an oropharyngeal and normal skin swab, a saliva sample and

a dried blood spot (DBS) will be taken, data collected on socio-demographics, social-mixing/behavioural factors and clinical examination findings. Swabs will also be taken from any pyoderma lesions, environmental swabs from common touch points and settle plates used inside households. In addition, a blood for a serum sample will be taken at the enrolment and final visits.

A subgroup of 16 random households, will undergo more frequent (weekly) throat and skin swabbing for a period of 6 weeks, during the second 6 months of the study.

Weekly swabs will also be taken from participants who become GAS (or GCS/GGS) carrier positive within the first 6 months, until they have had 2 negative swabs.

Participants reporting symptoms suggestive of possible clinical GAS infection such as pharyngitis or pyoderma (but also including invasive infections), will be visited for an unscheduled visit where a clinical and health-seeking history will be recorded, a swab, a saliva sample and a DBS taken, and treatment (or further management) will be delivered according to WHO guidelines.

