3.2 Sub-studies

3.2.1 Intensified incident GAS surveillance cohort

A subgroup of 16 randomly selected households will form a cohort to undergo intensified swabbing. This cohort will be used to assess incidence and duration of GAS carriage and disease with greater resolution than the main cohort. All household members present will undergo more frequent swabbing (OPS and NSS), with a view to being visited every week for 6 weeks. At these visits, more detailed social-mixing behaviour data will be collected. This more intensive temporal epidemiology with the social-mixing behavioural data collected will be combined with WGS data to inform the household transmission model.

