3.2.2 Estimating duration of GAS carriage

A further subgroup will also be identified to allow for greater resolution in the estimation of the duration of GAS (and GCS/GGS) carriage. Following MV0, any participant who becomes GAS (or GCS/GGS) carrier positive (i.e. was negative at baseline or the previous visit, and then becomes positive at a monthly visit) will have weekly swabs taken from the same site that was positive, until 2 GAS negative swabs have been taken in a row.

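### New carriers in the 16 intensified households are excluded from weekly swabbing to two negatives, and no rule continues their weekly swabs after the six-week block, so duration to the nearest week is incomplete for between none and 36% of new carriers, depending on how the exclusion is read

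*Protocol*

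**What the plan says.** Duration of asymptomatic throat and skin carriage, to the nearest week, is a primary endpoint (Protocol, section 2.1). Five places bear on how it is observed.

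- Section 3.2.2 starts weekly swabs of the positive site for "any participant who becomes GAS (or GCS/GGS) carrier positive" after the enrolment visit, and stops them after two negatives in a row.
- Section 5.3.6 states the same procedure, with new carriers "swabbed weekly until such time as 2 negative swabs in a row have been obtained from the same site that was positive", but opens with a restriction: "All participants not already in the intensified incident GAS cohort". Both sections define a new carrier by a positive swab at a monthly visit, and neither gives an end date.
- Section 3.2.1 assigns the 16 intensified households to the duration question as well: "This cohort will be used to assess incidence and duration of GAS carriage and disease with greater resolution than the main cohort".
- Section 5.3.5 fixes the length of their weekly swabbing: "These households will be visited up to every week for 6 weeks during the second half of the study". Regular monthly visits continue alongside.
- The Protocol summary (Description of Study Design) adds timing. For new carriers: "Weekly swabs will also be taken from participants who become GAS (or GCS/GGS) carrier positive within the first 6 months". For the intensified households: "more frequent (weekly) throat and skin swabbing for a period of 6 weeks, during the second 6 months of the study".

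No section gives the intensified households a rule of their own for following a carrier to two negatives, and none says when the 16 households are selected.

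**The concern.** Sections 3.2.2 and 5.3.6 describe the same sub-study and disagree on who is in it. The excluded households are also a declared source of duration data, yet their weekly swabbing ends on a calendar limit and not on clearance.

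Two things are at stake. First, if field staff treat the 16 households as members from early in the study, their new carriers never enter weekly follow-up and the duration cohort shrinks. Second, on any reading, a carrier found during the block and still positive at week 6 drops back to monthly swabs. Table 1 (section 5.4) allows 14 days either side of a monthly visit, so the end of such an episode cannot be placed to the nearest week.

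**Working it through.** **Plan's own figure.** The protocol gives no sample size for duration. Its only calculation is for prevalence (section 8), and it reproduces: 1.96² × 0.15 × 0.85 / 0.05² = 195.9, so 196; × 2 for the design effect = 392; × 1.10 for drop-out = 431.

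**Inputs.** 45 households and about 450 people, with incidence 20% per year (section 8); 16 intensified households (3.2.1, 5.3.5, Table 1); a block of 6 weeks (5.3.5). I count each incident case as one new-carrier episode.

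**Share of the sample.** 16/45 = 35.6%, about 160 people. Expected new carriers per year: 450 × 0.20 = 90.

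**Loss caused by the exclusion, by reading.**

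| When the exclusion applies | Share affected | New carriers without weekly follow-up to two negatives |
|---|---|---|
| Whole study | 35.6% | 90 × 16/45 = 32 of 90 per year |
| From the start, new-carrier rule limited to the first 6 months | 35.6% | 45 × 16/45 = 16 of 45 |
| Only during the block, rule running all year | 35.6% × 6/52 = 4.1% of person-time | 160 × 0.20 × 6/52 = 3.7 |
| Summary timing, households not yet counted as members in the first half | 0% | 0 |

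If only the 85% not carrying are at risk, the first row becomes about 27 of 77 (450 × 0.85 × 0.20 = 76.5; × 16/45 = 27.2). On the whole-study reading 29 households remain, and the standard error rises by √(45/29) = 1.25. The block count of 3.7 becomes 2.8 at 15% incidence and 5.9 at 32%.

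**Loss caused by the fixed six-week end.** I simulated acquisition at a uniform time within the block, weekly swabs at weeks 1 to 6, perfect detection and exponential carriage durations. The protocol gives no mean duration, so the means are assumptions shown as a range.

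| Assumed mean duration (weeks) | Detected episodes without two consecutive negatives by week 6 |
|---|---|
| 2 | 56% |
| 4 | 71% |
| 8 | 82% |
| 12 | 88% |

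Part of this is structural: an episode first found at week 5 or 6 cannot show two later negatives by week 6, however short it is.

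**Household count.** The appendix schedule of events labels the incidence cohort as 12 households. On that figure the top of the range would be 12/45 = 26.7%. This also needs reconciling.

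**The case against.** The strongest objection is timing. The summary puts the new-carrier rule in the first six months and the block in the second. If a household is a member only once its block starts, no first-half carrier is excluded and the exclusion costs nothing. This stands as one possible reading. It is not secured by the text: sections 3.2.2 and 5.3.6 carry no six-month limit and the selection date is not given. Table 1 gives the incidence cohort its own column at monthly visits from MV1, and section 5.5.2 asks this cohort more detailed questions at each monthly visit. Both fit membership from early on.

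A reader might infer that a third of the sample is lost to the duration endpoint. The documents do not support that. It needs exclusion from the start of the study, and even then these households keep monthly throat and skin swabs. Their episodes are interval-censored, long carriage is still seen, and what is missing is weekly resolution.

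A reader might also infer that the intensified cohort cannot measure duration as section 3.2.1 says. That section promises better resolution than the monthly main cohort, and inside the block weekly swabs deliver it.

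Finally, a reader might infer bias towards short carriage. The 16 households are chosen at random, so leaving them out costs mainly precision. Bias arises only if completed episodes are analysed alone. The protocol does not say they will be, and handling of censoring may properly sit in the analysis plan.

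**Conclusion.** The point holds in a limited form. Sections 3.2.2 and 5.3.6 contradict each other on who is followed weekly to two negatives, and nothing continues weekly swabs for a block participant still positive at week 6.

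The exclusion removes weekly-resolution data for none to 36% of new carriers, and the text does not settle where in that range the study falls. The counts rest on the protocol's 20% incidence and an average household of 10. The proportions still open at week 6 rest on exponential durations, perfect swab sensitivity and the assumed means; longer carriage makes them larger. A censoring-aware analysis can use unfinished episodes correctly, but it cannot supply weekly observations that were never taken. That is why this should be settled in the protocol.

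**What to change.** Reconcile the summary with sections 3.2.2, 5.3.5 and 5.3.6:

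1. Delete the exclusion in 5.3.6, or limit it to the weeks in which the household is actually under weekly swabbing.
2. State whether the new-carrier rule runs for 6 or 12 months, and when the 16 households are selected. If the six-month limit stays, say expressly that carriers found in the block are an exception; otherwise item 3 would contradict the limit.
3. For any new carrier found during the block, at a weekly or a monthly visit, continue weekly swabs of the positive site after week 6 until two consecutive negatives. Weekly visits must be named, because 3.2.2 and 5.3.6 recognise only a positive at a monthly visit.
4. Treat episodes still unfinished as right-censored or interval-censored.
5. Correct the household count in the appendix schedule or in the body.

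The cost is a small number of single-site weekly swabs by the separate weekly team that section 5.3.1 already provides. At 20% incidence about 3 to 4 carriers would be found in the block, and more if incidence is higher. Weekly follow-up of new carriers restored outside the block comes on top: at most about 28 a year on the whole-study reading (32 − 3.7), and none if the exclusion was only ever meant for the block.
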